10.1.2 Serious adverse events

An SAE is defined as any AE (appearance of (or worsening of any pre-existing) undesirable sign(s), symptom(s) or medical conditions(s)) which meets any one of the following criteria:

- Fatal
- Life threatening
 - Life threatening in the context of a SAE refers to a reaction in which the patient was at risk of death at the time of the reaction; it does not refer to a reaction that hypothetically might have caused death if it were more severe (please refer to the ICH-E2D Guidelines).
 - Results in persistent or significant disability/incapacity
 - Constitutes a congenital anomaly/birth defect
 - Requires inpatient hospitalization or prolongation of existing hospitalization, unless hospitalization is for:
 - Routine treatment or monitoring of the study indication not associated with any deterioration in condition.
 - Elective or pre-planned treatment for a pre-existing condition that is unrelated to the indication under study and has not worsened since signing the informed consent
 - Social reasons and respite care in the absence of any deterioration in the patient’s general condition
 - Treatment on an emergency outpatient basis for an event not fulfilling any of the definitions of a SAE given above and not resulting in hospital admission

- Is medically significant, e.g. defined as an event that jeopardizes the patient or may require medical or surgical intervention to prevent one of the outcomes listed above.

Medical and scientific judgment should be exercised in deciding whether other situations should be considered serious reactions, such as important medical events that might not be immediately life threatening or result in death or hospitalization but might jeopardize the patient or might require intervention to prevent one of the other outcomes listed above. Such events should be considered as “medically significant”. Examples of such events are intensive treatment in an emergency room or at home for allergic bronchospasm, blood dyscrasias or convulsions that do not result in hospitalization or development of dependency or abuse (please refer to the ICH-E2D Guidelines).

All malignant neoplasms will be assessed as serious under “medically significant” if other seriousness criteria are not met.

Any suspected transmission via a medicinal product of an infectious agent is also considered a serious adverse reaction.

All reports of intentional misuse and abuse of the product are also considered serious adverse event (SAE) irrespective if a clinical event has occurred.

10.1.3 Protocol exemption from reporting

In this study, nAMD recurrences and their clinical manifestations are exempt from reporting. Patient treatment is based on disease activity, which is assessed and recorded throughout the study in the eCRF. Moreover, nAMD is a progressive disease while its treatment is a non-continuous drug administration so disease activity might mean that a patient needs more frequent dosing rather than lack of efficacy.

10.1.4 SAE reporting

To ensure patient safety, every SAE, regardless of causality, occurring after the patient has provided informed consent and until the last study visit or 30 days after the last administration of study treatment whichever is later must be reported to Novartis safety immediately, without undue delay, under no circumstances later than within 24 hours of learning of its occurrence. Detailed instructions regarding the submission process and requirements are to be found in the Investigator folder provided to each study site.

All follow-up information for the SAE including information on complications, progression of the initial SAE and recurrent episodes must be reported as follow-up to the original episode within 24 hours of the Investigator receiving the follow-up information. An SAE occurring at a different time interval or otherwise considered completely unrelated to a previously reported one must be reported separately as a new event.

If the SAE is not previously documented in the IB or Package Insert (new occurrence) and is thought to be related to the study treatment, a Chief Medical Office & Patient Safety (CMO & PS) Department associate may urgently require further information from the Investigator for health authority reporting. Novartis may need to issue an Investigator notification (IN) to inform all Investigators involved in any study with the same study treatment that this SAE has been reported.

Suspected unexpected serious adverse reactions (SUSARs) will be collected and submitted to the Competent Authorities and relevant Ethics Committees in accordance with EU Guidance 2011/C 172/01 or as per national regulatory requirements.

Any SAE occurring after the patient has provided informed consent and until the last study visit or 30 days after the last administration of study treatment whichever is later will be reported.

Any SAEs experienced after the above mentioned period should only be reported to Novartis Safety if the Investigator suspects a causal relationship to study treatment.

10.1.5 Pregnancy reporting

Women of childbearing potential are excluded from this study.

To ensure patient safety, each pregnancy occurring after signing the informed consent must be reported to Novartis within 24 hours of learning of its occurrence (female participants only).

The pregnancy (for female participants) should be followed up to determine outcome, including spontaneous or voluntary termination, details of the birth, and the presence or absence of any birth defects, congenital abnormalities, or maternal and/or newborn complications.

Pregnancy should be recorded and reported by the Investigator to the Novartis CMO & PS Department. Pregnancy follow-up should be recorded on the same form and should include an assessment of the possible relationship to brolucizumab (investigational) with any pregnancy outcome.

Any SAE experienced during pregnancy must be reported.

10.1.6 Reporting of study treatment errors including misuse/abuse

Medication errors are unintentional errors in the prescribing, dispensing, administration or monitoring of a medicine while under the control of a healthcare professional, patient or consumer (European Medicines Agency definition).

Study treatment errors and uses outside of what is foreseen in the protocol will be collected in the dose administration record in the eCRF and in the Dispensing Log at the study site, irrespective of whether or not associated with an AE/SAE and reported to Safety only if associated with an SAE.

Table 10-1 Guidance for capturing the study treatment errors including misuse/abuse

Treatment error type	Document in dose administration eCRF (Yes/No)	Document in AE eCRF	Complete SAE form
Unintentional study treatment error	Yes (only date and time of injection)	No	Only if associated with an SAE

For more information on AE and SAE definition and reporting requirements, please see the respective sections ([Section 10.1.1](#), [Section 10.1.2](#) and [Section 10.1.3](#)).

11 Data collection and database management

11.1 Data collection

Designated Investigator staff will enter the data required by the protocol into the eCRFs, which have been built using fully validated secure web-enabled software that conforms to 21 CFR Part 11 requirements. Study site staff will not be given access to the EDC system until they have been trained. Automatic validation programs check for data discrepancies in the eCRFs, allow modification and/or verification of the entered data by the Investigator staff.

The Investigator/designee is responsible for assuring that the data (entered into eCRF) is complete, accurate, and that entry and updates are performed in a timely manner. The Investigator must certify that the data entered are complete and accurate.

After final database lock, the Investigator will receive copies of the patient data for archiving at the study site.

All data must be recorded, handled and stored in a way that allows its accurate reporting, interpretation and verification.

11.2 Database management and quality control

Novartis (or designated CRO) personnel will review the data entered by investigative staff for completeness and accuracy. Electronic data queries stating the nature of the problem and requesting clarification will be created for discrepancies and missing values and sent to the study site via the EDC system. Designated Study site staff are required to respond promptly to queries and to make any necessary changes to the data.

Concomitant treatments and prior medications entered into the database will be coded using the World Health Organization (WHO) Drug Reference List, which employs the Anatomical Therapeutic Chemical classification system. Medical history/current medical conditions and AEs will be coded using the Medical Dictionary for Regulatory Activities (MedDRA) terminology.

Ocular images will be handled as described in [Section 8.3.1](#) and [Section 8.3.2](#). The Data management staff will review data received from the CRC. Data review will be done for data structure and data completeness/accuracy as defined in Vendor Data Transfer Specifications.

The occurrence of relevant protocol deviations will be determined at Week 16 before the interim database lock for the primary analysis and at the conclusion of the study. Once all the necessary actions have been completed and the database has been declared to be complete and accurate, it will be locked. Any changes to the database after that time can only be made after written agreement by Novartis development management.

11.3 Site monitoring

Before study initiation, at a study site initiation visit or at an Investigator's meeting, a Novartis/ designated CRO representative will review the protocol and data capture requirements (i.e. eSource DDE or eCRFs) with the Investigators and their staff. During the study, Novartis employs several methods of ensuring protocol and GCP compliance and the quality/integrity of the study sites' data. The field monitor will visit the study site to check the completeness of

patient records, the accuracy of data capture/data entry, the adherence to the protocol and to GCP, the progress of enrollment, and to ensure that study treatment is being stored, dispensed, and accounted for according to specifications. Key study personnel must be available to assist the field monitor during these visits. Continuous remote monitoring of each study site's data may be performed by a centralized Novartis/ designated CRO. Additionally, a central analytics organization may analyze data & identify risks & trends for study site operational parameters, and provide reports to Novartis clinical teams to assist with study oversight.

The Investigator must maintain source documents for each patient in the study, consisting of case and visit notes (hospital or clinic medical records) containing demographic and medical information, retinal images (██████████ OCT), and the results of any other tests or assessments. All information on eCRFs must be traceable to these source documents in the patient's file. The Investigator must also keep the original ICF signed by the patient (a signed copy is given to the patient).

The Investigator must give the monitor access to all relevant source documents to confirm their consistency with the data capture and/or data entry. Novartis monitoring standards require full verification for the presence of informed consent, adherence to the inclusion/exclusion criteria, documentation of SAEs, and of data that will be used for all primary variables. Additional checks of the consistency of the source data with the eCRFs are performed according to the study-specific monitoring plan. No information in source documents about the identity of the patients will be disclosed.

12 Data analysis and statistical methods

The primary efficacy analysis will be based on the Week 16 data, i.e. data up to and including Week 16. This analysis will be performed once all patients have completed their Week 16 visit or prematurely discontinued the study before/on their Week 16 visit, while patients will continue to receive study treatment until their Week 44/Week 46 visit, dependent on their treatment schedule. The analysis of the data after the EOS (Week 48/50) visit will be performed once all patients have completed or prematurely discontinued the study.

Any data analysis carried out independently by the Investigator should be submitted to Novartis before publication or presentation.

In addition to the statistical methods outlined below, further details will be described in the Statistical Analysis Plan (SAP).

██████████

12.1 Analysis sets

The Enrolled Set (ENS) includes all patients who signed an ICF and are assigned patient numbers.

The Safety Set includes all patients who received at least one IVT injection of study treatment.

The Full Analysis Set (FAS) will be the same as the Safety Set in this study and will be used as primary population to analyze the efficacy endpoints.

The Per-Protocol Set (PPS) is a subset of patients of the FAS without PDs with impact. The list of PD criteria will be provided in a separate document.

However, when assessing the robustness of the overall efficacy conclusions, considerations will be given to the analysis based on the estimand using FAS and PPS. Expectation of comparing of both estimands is to have similar conclusions. Inconsistencies in the results will be examined and discussed in the Clinical Study Report (CSR).

12.2 Patient demographics and other baseline characteristics

Demographic and other Screening/Baseline data including disease characteristics will be listed and summarized descriptively for the FAS.

Categorical data will be presented as frequencies and percentages. For continuous data, n, mean, standard deviation, median, 25th and 75th percentiles, minimum, and maximum will be presented.

Relevant medical histories and current medical conditions at Screening/Baseline will be listed.

The last available assessment taken prior to the first IVT injection of study treatment is taken as the “baseline” assessment.

12.3 Treatments

The Safety set will be used for the analyses below. Categorical data will be summarized as frequencies and percentages. For continuous data, mean, standard deviation, median, 25th and 75th percentiles, minimum, and maximum will be presented.

The extent of exposure to study treatment as number of IVT injections received from Screening/Baseline to the end of the treatment period will be descriptively summarized. Furthermore, the number of patients in each injection category (1 injection, 2 injections up to the maximum number of injections) from Screening/Baseline to the end of the treatment period will be presented.

The dosing regimen received at W48 will be presented descriptively.

Prior medications are defined as treatments taken and stopped prior to first IVT injection. Any medication given at least once between the day of first IVT injection and the date of the last study visit will be a concomitant medication, including those which were started pre-Screening/Baseline and continued into the period where study treatment is administered.

Concomitant medications and significant non-drug therapies prior to and after the start of the study treatment will be listed according to the Anatomical Therapeutic Chemical (ATC) classification system.

Anti-VEGF medications (other than the study treatment) will be summarized separately.

12.4 Analysis of the primary endpoint

12.4.1 Definition of the primary endpoint

The primary objective of this study is to evaluate the effect of brolucizumab 6 mg on disease control. The primary efficacy endpoint is the proportion of patients with no disease activity at Week 16. This analysis will be performed in the FAS and will focus on the study eye only.

12.4.2 Statistical model, hypothesis, and method of analysis

The number (%) and proportion of patients with no disease activity at Week 16 will be provided with the associated 95% confidence interval using Clopper-Pearson method.

12.4.3 Handling of missing values/censoring/discontinuations

For patients who:

- Discontinue study treatment but continue in the study, the efficacy data will be censored at the time the patient stopped study treatment in the study eye.
- Interrupt treatment, the efficacy data will be censored at the time the study treatment was first interrupted.

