Adverse events (AEs) of intraocular inflammation, including retinal vasculitis and/or retinal vascular occlusion have occurred since the Oct-2019 marketing authorization approval for brolucizumab (Beovu®) in the treatment of nAMD. These AEs may result in severe vision loss. Results of the mechanistic study BASICHR0049 of blood samples from nAMD patients exposed to brolucizumab and having subsequently developed Retinal Vasculitis (RV) and/or Retinal Vascular Occlusion (RO) taken together with accumulated data of the association of treatment-emergent immunogenicity and intraocular inflammation (IOI) indicate a causal link between the treatment-emergent immune reaction against brolucizumab and the brolucizumab-related “Intraocular inflammation, including retinal vasculitis and/or retinal vascular occlusion”. This finding supports the requirement to discontinue treatment with brolucizumab in patients who develop events of Intraocular inflammation, including RV and/or RO.

Based on clinical studies, IOI related adverse events, including retinal vasculitis and retinal vascular occlusion, were reported more frequently in female patients treated with brolucizumab than male patients (e.g. 5.3% females vs. 3.2% males in HAWK and HARRIER, Novartis data on file).

In addition, based on USM (CRTH258AUS04 FIR), the brolucizumab dosing interval should not be less than 8 weeks beyond the loading period.

Intravitreal injections, including those with brolucizumab, have been associated with endophthalmitis and retinal detachment. The injection procedure must be carried out under aseptic conditions. Patients should be instructed to report any symptoms suggestive of the above-mentioned events immediately.

Transient and sustained increases in intraocular pressure (IOP) have been seen with brolucizumab, similar to those observed with IVT administration of other VEGF inhibitors. Both IOP and perfusion of the optic nerve head must be monitored and managed appropriately.

Brolucizumab must not be administered in case of hypersensitivity to the active substance or to any of the excipients, active or suspected ocular or periocular infection, or active intraocular inflammation (IOI).

Appropriate eligibility criteria are included in this protocol. The risk to patients in this study may be minimized by compliance with the eligibility criteria and study procedures, as well as close clinical monitoring described in [Section 6.7.2](#), [Section 8.4.4](#) and [Section 10](#).

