14) The week 48/50 EOS assessments only apply to patients who completed the study per protocol. The assessments are not required for subjects who have undergone ETD assessments and continued in the study without study treatment.

15) ETD: Early treatment discontinuation applies to subjects who discontinue early from study treatment and continue in the study. The assessments should be performed 4 weeks after the last injection of study drug. This can occur at any time point.

16) For patients who continue in the study after ETD and up to Week 48/50 (end of study) while patient is on standard of care. Additional safety assessments and imaging can also be performed if required, as per investigators discretion. In addition, after ETD, subjects are not required to attend the mandatory visits at Week 16 and Week 48/50. The last visit should be at week 48. This can occur at any time point.

Assessments in the fellow eye

The fellow eye will be examined (data collected and analyzed) only at the Screening/Baseline and the Week 48/EOS visits as follows:

- At Screening/Baseline: BCVA, ophthalmic examination, [REDACTED] OCT, [REDACTED].
- At Week 48/EOS: BCVA, ophthalmic examination, [REDACTED] OCT [REDACTED].

Other assessments of the fellow eye may be performed at the Investigator's discretion in accordance with routine practice at other time points; however, these will not be collected or analyzed in this study.

All data obtained from these assessments must be supported in the patient's source documentation.

Concerning Odysight® optimal self-assessment, only best-corrected near visual acuity (BCNVA) for the study eye will be analyzed. It is not requested for the purpose of this study to do any self-assessment measure of the fellow eye.

Unscheduled visits

For patients who return to the study site before the next scheduled study visit, the Investigator will capture the unscheduled visit in the eCRF only in the case of a clinically significant abnormality finding.

If this finding leads to an AE and/or the decision to treat the patient prior to the next scheduled treatment, all the procedures listed for the interim visit need to be conducted and captured in the eCRF.

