9.1 Discontinuation

9.1.1 Discontinuation of study treatment

Discontinuation of study treatment for a patient occurs when study treatment is stopped earlier than the protocol planned duration and can be initiated by either the patient or the Investigator.

The Investigator must discontinue study treatment for a given patient if he/she believes that continuation would negatively affect the patient's well-being.

The Investigator and/or referring physician will recommend the appropriate follow-up medical care, if needed, for all patients who are prematurely withdrawn from the study.

Study treatment must be discontinued under the following circumstances:

- Patient requires treatment on a q4w interval after the initiation phase (Week 14/Week16), i.e., after the three-monthly injections at Baseline, Week 4, and Week 8, followed by the first interval extension

- Patient develops intraocular inflammation, including retinal vasculitis and/or retinal vascular occlusion
- Patient/guardian decision
- Pregnancy
- Use of prohibited treatment
- Any situation in which study participation might result in a safety risk to the patient

If premature discontinuation of study treatment occurs, the following should be done as appropriate:

- The Investigator should make a reasonable effort to understand and document the primary reason for the patient's premature discontinuation of study treatment using the appropriate eCRF page.
- Patients who prematurely discontinue study treatment for any reason should return 4 weeks after last study treatment to perform the assessments for early treatment discontinuation (ETD). Please refer to [Table 8-1](#), except for patients who withdraw their consent from the study and do not wish to do so (refer to [Section 9.1.2](#)).
- After these assessments are performed, patient can be switched to standard of care (SOC) anti-VEGF IVT as per investigators discretion. IVT injection is contraindicated in patients with active intraocular or periocular infections and in patients with active intraocular inflammation; therefore, the investigators must verify that these conditions are not present in the study eye prior to every injection.
- After premature study treatment discontinuation, at a minimum till week 48, in abbreviated visits, the following data should be collected at clinic visits or via telephone/email contact:
 - New/concomitant treatments
 - Adverse events/Serious Adverse Events
 - BCVA

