Percent change from Baseline: The percent change from baseline will be calculated as below: $((\text{post-baseline value} - \text{Baseline value}) / \text{Baseline value}) * 100$.

Proportion: A proportion refers to the fraction of the total that possesses a certain attribute. In this study attribute is disease free activity.

Disease control: When patients have no disease activity after taking study treatment then patient will be consider as disease control.

On-treatment period: The on-treatment period lasts from the date of first administration of study treatment to 30 days after the date of the last actual administration of any study treatment.

Treatment duration: The maximum planned duration of treatment for each patient is 44 to 46 weeks in accordance with the designated treatment regimen. Discontinuation of study treatment for a patient occurs when study treatment is stopped earlier than the protocol planned duration and can be initiated by either the patient or the investigator.

Treatment discontinuation: When patients discontinue study treatment but continue in the study, the efficacy data will be used at the time the patient stopped study treatment.

Last interval: The last treatment interval (defined by the investigator) before Week 48.

Maximum interval: The longest interval of treatment reached by the patient over the study period.

Event for no disease activity: When patients will be with no disease status as per investigator decision after last dose in initiation phase then the patients will consider as event for no disease activity. If patients with active disease status or early discontinue then patients will be considered as censored for disease activity.

Dry retina: Absence of fluid (IRF/SRF/ sub-RPE) will be considered as dry retina.

Event for dry retina: When patients have absence of fluid then it will be considered as an event of dry retina. If patients have a presence of fluid before/at EOS or early discontinuation then will be censored.

[figure not shown]
Study eye and fellow eye: The investigator selects the eye with the worse BCVA at Screening as the study eye if both eyes are eligible as per the inclusion and exclusion criteria, unless the investigator deems as a study eye more appropriate to select the eye with better BCVA, based on medical reasons or local ethical requirements. If both eyes are eligible as per the inclusion and exclusion criteria, then it is recommended to select the right eye as the study eye.

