2.7.1.4 Function outcomes (Best Corrected Visual Acuity (BCVA))

Summary statistics (n, mean, std, median, min and max) of BCVA for nAMD patients will be presented along with change from Baseline in BCVA by visit along with first anti-VEGF Treatment BCVA.

The above analysis will be done on the FAS and only on the study eye.

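### BCVA is to be collected to Week 48 after early treatment stop, but no efficacy analysis is assigned the post-stop values, and some mandatory reasons for stopping are related to outcome

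*Protocol*

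**What the plan says.** **Collection.** Protocol 9.1.1 provides: "After premature study treatment discontinuation, at a minimum till week 48, in abbreviated visits, the following data should be collected". The list that follows includes BCVA. In Table 8-1 the BCVA row is marked in the last column (m), and footnote 16 defines that column: "For patients who continue in the study after ETD and up to Week 48/50 (end of study) while patient is on standard of care".

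**Stopping.** Protocol 6.1.4 and 9.1.1 make stopping mandatory when intraocular inflammation (IOI) develops, including retinal vasculitis (RV) or retinal vascular occlusion (RO). It is also mandatory when a patient needs four-weekly treatment after the initiation phase. Protocol 4.5 says of the inflammatory and vascular events: "These AEs may result in severe vision loss".

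**Handling after the stop.** Protocol 12.4.3 states, for patients who stop treatment but stay in the study, that "the efficacy data will be censored at the time the patient stopped study treatment in the study eye". For the other case it states: "Interrupt treatment, the efficacy data will be censored at the time the study treatment was first interrupted". The final SAP, under general definitions (2.1.1), says instead that "the efficacy data will be used at the time the patient stopped study treatment". SAP Section 4 reports no change from the protocol analyses.

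**The BCVA analysis.** Protocol 8.3 lists BCVA as an efficacy assessment. Protocol 12.5.4 asks for summary statistics of the change at Week 48. SAP 2.7.1.4 gives summary statistics "along with change from Baseline in BCVA by visit", in the FAS, for the study eye. Neither section has its own rule for discontinuation, imputation or sensitivity analysis.

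**The concern.** The plan collects visual acuity after treatment stops but gives those values no place in the functional endpoint. Some of the mandatory reasons for stopping are themselves outcomes of treatment: an inflammatory or vascular event that can cost vision, or disease that is not held at eight-week intervals. If values after the stop are left out, the Week 48 mean describes patients who tolerated the drug and stayed controlled. In a single-arm study no control group shows the same selection, so a reader could take that mean as the result for everyone who started treatment. Large individual losses are more exposed to this than the mean, because a few patients can account for most of them.

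**Working it through.** **1. The rules side by side.**

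| Place | What it implies for BCVA after the stop |
|---|---|
| Protocol 12.4.3 (under the primary endpoint, general wording) | Removed from the stop, or from the first interruption |
| SAP 2.1.1 (general definition) | Either data up to the stop are used, or the value at the stop is used |
| Protocol 12.5.4, SAP 2.7.1.4 | Silent |
| Protocol 12.4.4, SAP 2.6.1 (LOCF, missing as active) | Concern Week 16 disease activity only |
| SAP 2.9.1.1 (safety) | BCVA change after the end date of each type of adverse event of special interest (AESI) |

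The two general rules differ, but neither brings later BCVA into the efficacy summary. The AESI summary is tied to the end date of the event and not to Week 48. It omits patients who stop for need of four-weekly treatment, and it does not feed the functional endpoint.

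**2. The plan's own figure.** The documents give no SD, expected change or stop rate for BCVA. The only design calculation is for the Week 16 proportion: 1.96² × 0.30 × 0.70 / 0.055² = 266.7, so 267 against the stated 265 (half-width at 265 is 0.0552), and 265 / 0.90 = 294.4, so 295. It reproduces closely and has no bearing on BCVA.

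**3. Formula for the shift.** Let f be the share of patients whose Week 48 value is left out, and D the mean Week 48 change in the retained patients minus that in the omitted patients. Then

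retained mean − all-patient mean = f × D.

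**4. IOI stops only.** Protocol 4.5 gives IOI-related events in HAWK and HARRIER as 3.2% of men and 5.3% of women. Of 295 patients that is 295 × 0.032 = 9.4 to 295 × 0.053 = 15.6, so about 9 to 16. D is assumed to be 5 to 10 letters.

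- 0.032 × 5 = 0.16 letters
- 0.053 × 10 = 0.53 letters

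**5. All stops.** Both f (10% to 30%) and D (5 to 10 letters) are assumed.

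- 0.10 × 5 = 0.5
- 0.20 × 5 = 1.0
- 0.20 × 10 = 2.0
- 0.30 × 10 = 3.0 letters

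The design assumption of 25% to 35% without disease activity at Week 16 implies 65% to 75% with activity, or 192 to 221 of 295. An unknown share of these would need four-weekly treatment and stop, so stops for that reason could outnumber IOI stops.

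**6. Scale.** With an assumed SD of 8 to 13 letters, the 95% half-width for the mean change in 295 patients is 1.96 × 8 / √295 = 0.9 to 1.96 × 13 / √295 = 1.5 letters. The shift from IOI stops alone is smaller than this. The shift from all stops ranges from below it to about twice its upper end.

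**The case against.** **The rule may not govern BCVA.** Section 12.4.3 belongs to the primary endpoint, and Section 12.5 does not cite it. This stands in part: extending it to BCVA is a reasonable reading, not an explicit statement. But the wording is general, the SAP counterpart is a general definition, and nothing says that post-stop BCVA is to be used.

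**A reader might infer that the patients most likely to lose vision are excluded.** The documents do not support that. These patients remain in the FAS and contribute BCVA at every visit up to the stop. What is lost is their later values, including Week 48. If SAP 2.1.1 means that the value at the stop is kept, they would also be represented by that value.

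**A reader might infer that vision loss from inflammation goes unreported.** It does not: SAP 2.9.1.1 summarises and plots BCVA change for each AESI type, within the limits noted above.

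**A reader might infer that the endpoint is shown to be biased in the drug's favour.** It is not shown. Protocol 4.5 reports that over 90% of IOI events were mild to moderate and 79% resolved without sequelae. Patients who stop may move to standard-of-care anti-VEGF treatment, so a deficit of 5 to 10 letters at Week 48 is an assumption and could be smaller or reversed.

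**The data may be incomplete, and an on-treatment summary has a use.** Both stand. Table 8-1 footnote 16 and Protocol 9.1.1 do not require attendance at Week 48 after early discontinuation, although the footnote also says the last visit should be at that week. Telephone or email contact is allowed, and it cannot yield an ETDRS-chart score. SAP 2.2 keeps unscheduled visits out of by-visit tables. Post-stop BCVA also reflects another treatment, so an on-treatment summary is legitimate if it is labelled as one.

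**Conclusion.** The point holds as a gap in the analysis of planned data. BCVA is to be collected to at least Week 48 after early stop, no efficacy analysis uses the later values, and the protocol and SAP rules on post-stop data do not agree. Because stopping is mandatory for IOI, RV or RO and for need of four-weekly treatment, the Week 48 BCVA change would probably be summarised without values whose absence is related to outcome. A favourable shift is the likely direction, but the documents prove neither direction nor size. The shift is about 0.2 to 0.5 letters for IOI stops alone, using IOI rates from treatment-naive patients and an assumed deficit of 5 to 10 letters. It is 0.5 to 3.0 letters if 10% to 30% stop with that deficit, where both inputs are assumptions. The change should be made because it is cheap, not because a large bias has been demonstrated.

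**What to change.** - In SAP 2.7.1.4, add a summary of BCVA change from baseline at Week 48 in the FAS that uses all BCVA collected, whatever the treatment status. State that Protocol 12.4.3 does not apply to it.
- With it, give the number of patients losing 15 letters or more (an added descriptive count), and the number of stopped patients with and without a Week 48 BCVA. The last two counts show how far the all-data mean is itself selected.
- Show it beside an on-treatment summary labelled as such.
- Reconcile Protocol 12.4.3 with SAP 2.1.1: say whether post-stop efficacy data are removed or the value at the stop is kept, to which endpoints the rule applies, and whether BCVA at the early-discontinuation visit, four weeks after the last injection, counts as before or after the stop.

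**Cost.** One extra table from data the protocol already plans to collect, and a clarification of the text. The downside is that post-stop BCVA reflects standard-of-care treatment and may be incomplete, so the table needs a note saying so.
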